Real world applicability of a study is enhanced if exclusion criteria are kept to a minimum. However, clear confounds should be avoided. Miller, et al., found that in young surgical patients, diabetes, cancer, kidney disease, hypertension, and abnormal BMI all significantly increased the chances of wound complications, while COPD, smoking, age, and HIV status did not.⁸² Yang, et al., found that smoking, hypertension, age, diabetes, and obesity did not delay VLU healing, and that males were more likely to have delayed VLU healing.⁸³ In contrast, Lane, et al., found that smoking dramatically reduced pressure injury healing, and McDaniel and Browning found that smoking negatively impacts chronic wound healing by impairing neutrophil function and fibroblast activity; decreasing both white and red blood cell production; increasing carbon monoxide, hydrogen cyanide, and other toxic compounds; causing tissue hypoxia; and causing the release of catecholamines.^{84,85} Smoking cessation programs led to improved wound healing.^{84,85} Parker, et al., found that delayed venous ulcer healing was correlated with living alone, ulcer duration > 24 weeks, and age > 70 years.⁸⁶ A review of studies of venous leg ulcer management demonstrated that 12 weeks were sufficient to determine if a treatment was effective or not.⁸⁷

2. Research Questions/Aim:

This study's primary purpose is to determine if an *improvised dressing*, made from inexpensive materials available for purchase in rural as well as urban settings, is a safe and effective, culturally and medically acceptable choice for managing sickle cell leg ulcers in a tropical climate. Three research questions will be addressed:

(1) Is the *improvised dressing*, consisting of a cut-to-fit new plastic bag sealed at the periwound with zinc oxide paste, safe and effective (see definitions, below) when compared with usual practice (saline-soaked gauze) and when compared with an advanced wound dressing (PMD), on sickle cell leg ulcers (SCLUs) in Jamaica?

(2) Does use of the *improvised dressing*, when compared with usual practice, improve the quality of life of patients (decrease pain, increase ability to engage in desirable activities, decrease wound-related materials costs, decrease time required to perform dressing changes, improve Wound QoL scores, and improve ASCQ-Me pencil-and-paper interview scores) with SCLUs in Jamaica?

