(3) Is the *improvised dressing* culturally acceptable to health care providers, patients, and families for managing SCLUs in Jamaica?

The expected study outcome is improvised dressing superior effectiveness and quality of life, when compared with usual practice, without increased safety and acceptability issues.^{13,59,60,62} The improvised dressing is likely to be the least expensive choice, with the added benefit of being available as first aid treatment throughout Jamaica. The advanced dressing is likely to be more expensive with respect to materials costs, although fewer dressing changes are anticipated and pain medication expenses are likely to be reduced. Based upon the review of the literature, no serious infections or other safety issues are anticipated for any group. However, to ensure that complications are not overlooked, in addition to the onsite researchers' vigilance, weekly wound photos will be assessed for complications (signs of infection, wound deterioration, or clinically relevant maceration) by two off-site blinded wound experts, Drs. [name] and [name].

Definitions:

Sickle cell leg ulcer – a wound in a HbSS or HbS β^0 positive patient, open greater than one month,⁷ below the level of the knee excluding the plantar surface of the foot.

Closed wound -100% epithelialized with no discernible scab or exudate production (paper napkin remains dry when lightly pressed against area, and no recurrence in the subsequent two weeks)

Safe – infection and other complications (healing-impairing maceration, keloid, and contracture rates) not statistically significantly higher than usual practice, with no major adverse events attributable to the method

Effective – ulcer closure rates or ulcer surface area reduction rates not statistically significantly lower than usual practice

Acceptable – average acceptability scores of 4 or higher on a 1-5 scale

3. Methods and Materials

a. Study design

This study will be a targeted-blinded (the off-site wound experts and the local physicians verifying wound closure and/or complications will be blinded to the randomization group), randomized controlled trial with three arms: (1) usual practice (negative control), (2) the improvised dressing, and (3) the advanced dressing (positive control). The expected outcome is improvised and advanced dressing superiority.

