Although non-inferiority is an acceptable outcome for the improvised dressing, the review of the literature supports the expectation that it will outperform usual practice. This superiority study design eliminate the motive for the blinded evaluators to minimize differences between groups, biasing the results.¹³ If superiority is attained, the results will be evaluated with intent to treat (ITT) analysis.

If superiority is not demonstrated, the data for the improvised dressing and usual practice dressing will be re-evaluated to assess for noninferiority.¹³ Contrary to superiority trials where use of intention-to-treat is employed to protect against type 1 error, the appropriate approach for noninferiority trials is to use a per-protocol approach,¹³ which, at worst, would exaggerate the differences between treatment groups, thereby yielding a more conservative estimate in the setting of a noninferiority trial.¹³ Thus, only those patients completing treatment in the group to which they were randomized will be retained for any non-inferiority analyses (see appendix for further details).

b. Study population

Individuals diagnosed with sickle cell disease who have a SCLU and reside in the parishes of St. Catherine, St. Andrew, or Kingston parishes of Jamaica and respond to advertisements, recruitment phone calls, or flyers posted at the Sickle Cell Unit (SCU) clinic and UHWI prior to and during the enrollment period will be invited to participate in the study. Members of the UHWI surgical team will call all patients identified by the SCU as having had a SCLU within the past two years to invite them to participate in the study. Jamaican residents who otherwise qualify but who live outside the study area will be included only if they agree to provide their own transportation and faithfully attend all clinic visits.

c. Sample

Study participants must have HbSS or HbS β^0 sickle cell disease, be between the ages of 13 and 70, and have a chronic SCLU, defined as a wound in a patient with sickle cell disease that has been open for at least one month and is below the knee, excluding the plantar surface of the foot. All SCLUs on a single patient will be dressed with the same dressing protocol. The largest ulcer at initial presentation is the study SCLU. If two or more SCLUs in close proximity join into

an enlarged ulcer during the first four weeks of the study, the sum of the initial areas will be considered the initial wound size for calculation purposes.

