Decrease in SCLU surface area will be used to answer research question 1. Conducting a power analysis for this study is challenging because only one study of SCLUs has demonstrated a statistically significant outcome, and the effect size was obscured by high standard deviations, which is a common problem in studies of wounds.⁸ Improvised plastic dressings similar to the study dressings were used in 49 chronic pressure ulcers in elderly patients, which are often slow to close, if they heal at all.⁶⁰ These two studies demonstrated a significant difference with confidence intervals of 99% with ~25 patients per group. Based upon these sample sizes and the Central Limit Theorem, it is reasonable to set the minimum sample size for this study at 30 patients per group,.^{88,89}

d. Variables

Dependent Variables (measured weekly - tools and permissions in appendices):

- 1. Persistent wound pain (using the Faces Pain Scale Revised (FPS-R))
- 2. Procedural (dressing change) wound pain
- 3. Amount of pain medication taken, including a total number of morphine equivalents plus non-opioid pain medications
- 4. Approximate time spent standing, or sitting with leg dependent without compression (estimated hours per week)
- 5. Patient overall quality of life (assessed with the ASCQ-Me Emotional, Pain, Social Functioning, Stiffness, and Sleep Impact Short Forms)
- 6. Patient wound-specific quality of life (assessed with the Wound QoL tool)
- 7. Materials costs (estimated, using lowest retail costs on Amazon.com for items not on the UWI price sheets)
- 8. Time spent performing dressing changes
- 9. Wound complication rates (e.g., wound infection, healing impairing maceration, wound deterioration)
- 10. Change in wound surface area (measured in cm² electronically using software that automatically corrects for skew, such as HealthEPix or WoundMatrix)⁹⁰

Dependent Variables (measured one time, at graduation from study)

- 11. Wound closure time, in weeks (see definitions; verified two weeks later. Omit patients whose wounds did not fully close they are included in 10., above.)
- 12. Acceptability of dressing choice patient (5 point Likert scale and qualitative free response)
- 13. Acceptability of dressing choice family member (5 point Likert scale and qualitative free response)
- 14. Acceptability of dressing choice UHWI staff (5 point Likert scale and qualitative free response)

Independent Variables (documented at initial study visit):

1. Patient gender

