Weekly, de-identified photographs will be sent by the Principal Investigator to be viewed by two blinded wound experts ([name] and [name]) off site. If the blinded experts, or anyone else involved in the study, expresses concern that a patient is exhibiting signs of possible infection, maceration that is delaying healing, or wound deterioration, a physician at UHWI or the SCU who is not otherwise involved in the study will be asked to evaluate that patient. The patient's dressings will be removed prior to this evaluation so that their treatment group will not be revealed to the physician (the evaluation by the physician is thus blinded to treatment group). If the physician determines that the patient's condition has not improved with the prescribed treatments (e.g., antibiotics), the patient will be withdrawn from the study. Any

patient who transitions out of the group to which they were randomized for any reason will receive usual treatment for their ulcer for the remainder of their 12 week study period.

When the treatment personnel at UHWI or the blinded remote observers state that the patient's wound appears to be closed, a physician at UHWI or the SCU who is not otherwise involved in the study will be asked to evaluate that patient. The patient's dressings will be removed prior to this evaluation so that their treatment group will not be revealed to the physician. Wound closure is defined as 100% epithelialized with no discernible scab or exudate production (a paper napkin blotting the area remains dry). Patients will be reassessed two weeks later to verify that the wound was truly closed and did not immediately recur.

Patients who are diagnosed with wound closure or have completed the 12 week study period will be taken aside privately and asked to rate the acceptability of their treatment using a 5 point Likert Scale. A family decision-maker will also be privately asked to rate the acceptability of the treatment. One of the research team members will enter this basic acceptability data for the patient and the family on the patient's Data Collection Tool. At that point, the patient will graduate from the study. However, patients and families will be instructed to return to UHWI for follow-up if a complication or recurrence develops. Any delayed complications (e.g., recurrence within 3 months) will be recorded on the patient's Data Collection Tool by the nurse or physician to whom the patient reports it.

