As a token of appreciation from the research team and an incentive for patients to return for their study clinic visits, each participant will be presented with a 500JM phone card at the end of each of the three 4-week study periods.

All wound management supplies for all three groups will be donated. Shipping and handling fees will be paid by the Principal Investigator with funds from a Wound Healing Foundation grant. Tallies of supplies used at dressing changes will be priced using the cost of medical supplies purchased by the SCU to determine the estimated cost of the treatment supplies for each patient. The PMD rolls will be valued at \$26.99US.⁹⁸

The Principal Investigator will de-identify the data and compile it from the patient Data Collection Tools onto an Excel spreadsheet. This spreadsheet and the de-identified wound photographs will be backed up onto the Principal Investigator's second password protected hard drive via a secure internet connection at least weekly. Two encrypted USB drives containing the data, including wound photographs, will be updated weekly on an alternating schedule and stored in a securely locked file in [name] office in UWI Department of Surgery.

i. Statistical analysis

A consultant, [name], PhD, Senior Biostatistician at The University of Texas Medical Branch in Galveston, will undertake the analysis.

When all of the patients have completed the study, the remainder of the data from the deidentified Data Collection Tools will be transcribed into an Excel spreadsheet by the Principal Investigator. The data will then be evaluated by the biostatistician using the most recent version of SPSS. Groups will be compared with respect to each of the 14 dependent variables, taking into account any confounding from the 11 independent variables. Results will be reported using descriptive statistics (means, modes, medians, frequencies), student's t test, and ANOVA with 95% CIs, using intent-to-treat.¹³ If the improvised dressing does not attain statistical superiority to usual practice, 80% CIs will be calculated with drop-outs removed from the analyses to evaluate noninferiority.^{13, Appendix: From Oczkowski SJW} Complications will be evaluated both individually and collectively by collapsing the pertinent columns.

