Research questions (1) and (2) will be addressed by using analyses of covariance (ANCOVA) to determine if patients in the improvised dressing group (Group 2) had superior results (95% CI's will fall within *f*, the superiority margins) from usual practice (Group 1) or advanced dressings (Group 3), or, if this is not demonstrated, failed to vary significantly (80% CI's will fall within *f*, the inferiority margins) from usual practice (group 1) or advanced dressings (group 3) with respect to each of the dependent variables, controlling for relevant patient characteristics (the independent variables).

Research question (3) will be addressed with descriptive statistics across Likert items regarding endorsement of and concerns with use of the improvised dressing clinically or in future studies. Qualitative comments will be summarized across providers into content themes. Any differences between nurses, patients, family members, and physicians will also be explored and noted.

All health care providers at UHWI participating in the study will be surveyed to explore their concerns as well as their opinions about each dressing choice, using both qualitative open-ended and a quantitative question on a Likert scale. Results will then be shared with the participating clinical staff to provide them with the evidence concerning each of the three dressing protocols.

j. Data handling and record keeping

All study data will be transferred from written documents to the Principal Investigator's password protected electronic devices, de-identified, and then transmitted over secure internet connections to the backup hard drive in the USA. The paper study documentation and the two encrypted USB drives containing the raw data will be stored in a securely locked file in in [name] office in UWI Department of Surgery for a period of at least two years after the study has been published, after which they may be destroyed.

When all of the patients have completed the study, members of the UHWI research team will proofread the Excel spreadsheet with the de-identified data for transcription errors. This data will then be evaluated by the biostatistician using the most recent version of SPSS.

4. Ethical Considerations

This study will be approved by the Ethics Review Committee (ERC) at UWI and the Jamaican Ministry of Health (MOH) prior to its implementation. It will be listed on clinicaltrials.gov prior to the recruitment of the first study patient.

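### Safe and effective are defined by a non-significant difference from usual practice, so failing to detect harm counts as success, and this conflicts with the plan's own margin-based fallback

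*Combined protocol and SAP*

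**What the plan says.** Section 2 (Research Questions/Aim) asks in question 1 whether the improvised dressing is "safe and effective (see definitions, below) when compared with usual practice" and the advanced dressing. The Definitions that follow set the criteria:

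- **Safe**: infection and other complication rates "not statistically significantly higher than usual practice, with no major adverse events attributable to the method". The second half of *safe*, on major adverse events, is not a significance test and is not at issue here.
- **Effective**: this term requires "ulcer closure rates or ulcer surface area reduction rates not statistically significantly lower than usual practice".

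Other sections give a different route to the same answer:

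- Section 3a: "If superiority is not demonstrated, the data for the improvised dressing and usual practice dressing will be re-evaluated to assess for noninferiority". Only patients who complete treatment in their randomised group are kept for this step.
- Section 3i: "80% CIs will be calculated with drop-outs removed from the analyses to evaluate noninferiority". The main analysis is intent-to-treat with 95% CIs.
- Section 3i, on questions 1 and 2: superiority first, "or, if this is not demonstrated, failed to vary significantly (80% CI's will fall within *f*, the inferiority margins"), for each dependent variable. That covers complications (variable 9) and wound area (variable 10).
- Section 3c: "Decrease in SCLU surface area will be used to answer research question 1".

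The supplied text gives no value for f. Sections 3a and 3i refer to an appendix that was not supplied and may contain one.

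**The concern.** A non-significant difference shows only that the data could not separate the arms. Used as a pass criterion, it lets absence of evidence stand for evidence of absence, and it rewards small samples and noisy measurement. The margin-based fallback does not have this fault, but the definitions do not refer to it and no section says which rule decides. Two rules that can disagree on one data set leave the choice open until results are known.

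Section 1b gives possible wound infection in a tropical climate as the reason for testing under professional supervision, and it intends the result to support promoting the dressing in every care setting. A real excess of complications could therefore be reported as safe and carried to places with less supervision.

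**Working it through.** **Inputs from the documents.** About 30 per arm, with up to 120 recruited for 25% dropout (section 3f). This reproduces: 90 / (1 − 0.25) = 120, or 40 per arm. The 30 per group cannot be re-derived, because no power, effect size, SD or event rate is given.

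**Assumptions.** Complication rates are not given, so a wide range is used. Sidedness is not stated and *higher* is directional, so both versions are shown.

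**1. Chance that a true doubling passes.** For each pair of counts (x usual practice, y improvised), z = (y/n − x/n) / √[2p̄(1 − p̄)/n], with p̄ = (x + y)/2n. The dressing fails only if z exceeds 1.96 (two-sided 5%) or 1.645 (one-sided 5%), or if y > x and two-sided Fisher p ≤ 0.05. Summing exact binomial probabilities over all passing pairs, n = 30:

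| True rates | Chi-square, two-sided | Fisher, two-sided | One-sided z |
|---|---|---|---|
| 5% v 10% | 90% | 98% | 81% |
| 10% v 20% | 81% | 90% | 69% |
| 15% v 30% | 72% | 81% | 58% |
| 20% v 40% | 61% | 70% | 48% |
| 30% v 60% | 34% | 44% | 24% |

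A doubling passes more often than not when the usual-practice rate is below about 24%, 28% or 19% respectively (20%, 23% or 15% at 40 per arm).

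**2. Effect of sample size.** For 10% v 20% at 20, 30, 40 and 60 per arm, the pass chance is 86%, 81%, 75% and 67% (chi-square), or 77%, 69%, 65% and 54% (one-sided).

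**3. The two rules on one result: 3/30 v 7/30.**
- Section 2 rule: p̄ = 10/60, SE = √(2 × 0.1667 × 0.8333/30) = 0.0962, z = 0.1333/0.0962 = 1.39, two-sided p = 0.17. Fisher p = 0.30. Not significantly higher, so it passes.
- Section 3i rule: 80% Wilson limits are 4.9% to 19.2% and 15.0% to 34.5%. The Newcombe interval for the difference is 13.3 − √(8.35² + 9.22²) = +0.9 to 13.3 + √(11.12² + 5.07²) = +25.6 points. It fails for any f below about 26 points.
- The 95% CI is −6 to +32 points.

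**4. Area.** For a true deficit of 0.5 SD, t test with n = 30: noncentrality 0.5 × √(30/2) = 1.94 against a critical value of 2.00 (58 df). It passes 52% of the time two-sided, 39% one-sided. At 40 per arm the figures are 40% and 28%.

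**5. The *or* in *effective*.** Read literally, either endpoint is enough. With closure of 15% against 30% on usual practice and area 0.5 SD worse, power to detect each deficit is 0.28 and 0.49 (normal approximation). At least one endpoint passes in 1 − 0.28 = 72% of trials if detection is nested, and in 1 − 0.28 × 0.49 = 86% if independent.

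**6. A margin rule with the true excess exactly at the margin** (usual practice 10%, n = 30, Newcombe upper limit below the margin):

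| Margin | 95% CI rule says safe | 80% CI rule | Present rule, two-sided | Present rule, one-sided |
|---|---|---|---|---|
| 10 points | 2.0% | 10.3% | 81% | 69% |
| 15 points | 2.5% | 10.3% | 67% | 52% |
| 20 points | 2.7% | 11.0% | 50% | 35% |

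For 15 points at 20, 30 and 60 per arm, the 95% rule stays near 3%, while the present two-sided rule gives 76%, 67% and 42%.

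**The case against.** The strongest reply is that section 3i is the operative test and section 2 only a short form of it. Section 3i says how questions 1 and 2 will be addressed, and it glosses a failure to vary significantly as a CI lying inside a margin. On that reading failing to detect harm does not pass, and the fault is loose wording. The unseen appendix might state f and tie it to the definitions. But question 1 points to the definitions by name, they contain no margin or cross-reference, and the gloss itself equates two different things. A number for f alone would not settle which rule governs.

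Four narrower points have weight:

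- The 3/30 v 7/30 example assumes the same patients under both rules, whereas the significance test is intent-to-treat and the fallback drops non-completers.
- The *safe* list names infection, maceration, keloid and contracture but not deterioration, so the higher assumed rates may lie outside that definition.
- Each pass probability is for one unadjusted comparison. Testing complications singly and together, and the adverse-event condition, lower the overall chance of passing by an amount not quantified here. Covariate adjustment is not modelled.
- A 95% bound and an all-randomised safety set go beyond the minimum cure, which is to tie the definitions to one margin rule.

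Blinded photograph review and independent physician assessment help find individual cases, but they do not change the group-level pass rule.

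**Conclusion.** The concern holds and must be fixed, because it determines the answer to research question 1. As written, non-significance is the whole test of *effective* and the complication-rate part of *safe*. The supplied text does not reconcile this with the 80% CI rule.

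The logical fault depends on no assumed figure; its size does. At 30 per arm a doubled complication rate passes a single comparison between 24% and 98% of the time over the rates and tests tried, and more often than not at usual-practice rates below about 19% to 28%. The closure-or-area wording and the differing complication lists are side points that need clarifying but do not carry the conclusion.

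**What to change.** Before anyone sees outcome data by arm, redefine both terms by a confidence bound against a pre-stated margin, and use the same margin and confidence level in sections 2 and 3i.

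- **Safe**: the upper limit of the two-sided 95% CI for improvised minus usual practice, in the proportion with any complication, lies below the margin, with no attributable major adverse event. Analyse all randomised patients. Section 3h says that a patient whose condition "has not improved with the prescribed treatments (e.g., antibiotics), the patient will be withdrawn from the study", so a completers-only set can lose the worst outcomes.
- **Events**: list which count. *Safe* names keloid and contracture, while sections 3d and 3h name deterioration.
- **Effective**: the 95% CI for the difference in area reduction excludes the inferiority margin, with closure supportive. State how the *or* fits with section 3c.
- **Otherwise**: conclude *not established* and report the interval.

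The investigators choose and justify the margins; an excess smaller than the margin may rightly pass. If they keep the 80% CI, they should state that the error at the margin is then about 10%.

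The cost is wording and two numerical margins, with no extra enrolment. The drawback is limited precision. With 10% complications in both arms and 30 per arm, a truly equal dressing would be *not established* 82%, 59% or 32% of the time for margins of 10, 15 or 20 points with a 95% CI (51%, 28% or 13% with an 80% CI). At 40 per arm the 95% figures are 74%, 46% and 21%. The small sample remains the underlying limit, and the revised rule makes it visible.

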- Based upon previous studies and the Central Limit Theorem, an estimated 90 participants (~30 per group) may be required for the differences between groups to reach statistical significance.^{12,23,88,89,96} Up to 120 patients will be recruited to allow for a 25% dropout rate. Based upon the literature review, pain, costs, wound size, and quality of life are expected to be significantly improved using the improvised dressings. However, because SCLUs are, historically, very slow to heal and often enlarge, complete wound closure is not an expected outcome for all patients.

g. Procedures for recruitment and consent

The study will be advertised using free community information channels such as church bulletins and radio outlets. Social media sites such as the CAIHR Facebook page will also be employed. Qualifying patients in the SCU database from up to two years prior to the study initiation will be called by the UHWI surgical team, alerting them to the dates for registering to participate. Flyers will be posted at the SCU in advance. Consent will be obtained by a member of the research team while the potential participant is waiting to be seen for wound care.

h. Data collection

The site for this study is the surgical clinic dressing area at the University Hospital of the West Indies (UHWI), Mona, Jamaica. The adjacent Sickle Cell Unit (SCU) will refer any SCLU patients to UHWI during the study period. UHWI is consistently well staffed with competent Jamaican health professionals. The UHWI surgical team will lead the study. Relatively few Jamaicans live or work in air-conditioned environments, ^[data in appendices] allowing the results from this out-patient population to translate to less developed tropical countries.

To ensure consistency, members of the research team will practice until they can demonstrate competency with all three dressing change procedures and with explaining the study forms prior to study patient recruitment.

Enrollment in the study will begin within two weeks of the day the Principal Investigator arrives at the Mona campus and will close 60 days later, or when a maximum of 120 patients have enrolled. All sickle cell positive patients presenting to UHWI with lower leg ulcers during the enrollment period will be screened for eligibility to enter the study. Each patient's data will be recorded for a total of 12 weeks, or until their SCLU has been closed for 2 weeks, whichever comes first.

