SCLUs are often disabling, scarring, and exquisitely painful. The research literature suggests that both the improvised dressing and the advanced dressing can decrease pain. The advanced dressing has also been shown to decrease scarring. However, children ages 13 - 18 are an especially vulnerable population. They are included in the study because this is the peak age group for SCLU formation, and therefore they are the most likely to benefit if the results can be generalized to them.¹⁵

5. Limitations

Blinding is a challenge inherent to studies of wounds. Although the the healthcare professionals who will monitor and verify wound closure and complications (outcomes) will be blinded, it is not possible to blind the participants or the research team members, because they will provide the wound management in this study.

Despite the incentives to remain in the study (phone cards monthly and wound management supplies at the conclusion of the study), it is possible that there will be a substantial dropout rate, because it is easy for patients with SCLUs to become discouraged, and they may feel that they have derived the major benefits of joining the study after the first few weeks.

All of the published studies of improvised dressings describe wound care performed by health professionals based in urban hospitals or long term care facilities. Although this study will be conducted in a tropical outpatient setting, it too is being conducted by health care professionals in an urban area. Also, Jamaica is significantly more developed than many of the countries for whom the improvised dressing educational program may be beneficial. Therefore, this study may not uniformly generalize to rural areas of tropical developing countries, where health professionals are absent.

6. Acknowledgments:

The researchers would like to thank all participants in the study.

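### The major-adverse-event part of 'Safe' is a zero-event rule in about 30 patients with no confidence limit and no comparison with usual practice, so a clean result would leave a rate of up to about 12% open

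*Combined protocol and SAP*

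**What the plan says.** The Combined protocol and SAP defines 'Safe' under Definitions in section 2, in two parts. Infection and other complications must be "not statistically significantly higher than usual practice, with no major adverse events attributable to the method". The first part compares arms. The second, "with no major adverse events attributable to the method", is a count that must be zero, and it takes in only events put down to the dressing.

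Research question 1, in the same section, asks whether the improvised dressing is safe when set against usual practice and against the advanced dressing. The text after the research questions expects no serious safety problem in any group.

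On numbers, section 3c says "it is reasonable to set the minimum sample size for this study at 30 patients per group", and section 3f says "an estimated 90 participants (~30 per group) may be required" and "Up to 120 patients will be recruited to allow for a 25% dropout rate".

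The safety item among the 14 dependent variables in section 3d is variable 9: "Wound complication rates (e.g., wound infection, healing impairing maceration, wound deterioration"). Section 3i compares the arms on each dependent variable with 95% confidence intervals and evaluates complications singly and pooled. It mentions no interval for major adverse events. The text reviewed neither defines a major adverse event nor names who decides that one is attributable.

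**The concern.** Safety is part of the study's primary purpose. Since the plan anticipates no serious safety issue, its expected result on this part is zero attributable major events, and the definition turns that result into 'safe' without qualification. An arm of this size cannot exclude an uncommon but important harm, and nothing in the definition obliges the report to say so.

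The missing comparator matters as well. For major events, the plan specifies no analysis that answers research question 1 as asked. A single event put down to the dressing would fail it even if usual practice had as many such events; with no event, it passes whatever happened in the control arm.

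The rationale in section 1b looks ahead to use by patients, families and lay providers before they reach a clinic. The strength of the safety statement will therefore count beyond this trial.

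**Working it through.** **Inputs.** About 30 patients per group (sections 3c and 3f); up to 120 recruited with 25% dropout (section 3f); zero attributable major events required (Definitions). No major-event rate is given, so the rates below are illustrative.

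**1. The plan's own figure.** 90 / (1 − 0.25) = 120, as stated. With equal groups, which the figure of about 30 per group implies, this is 120 / 3 = 40 recruited and 90 / 3 = 30 remaining per arm. The figure of 30 rests on earlier studies and the Central Limit Theorem; no event rate, power or bound for safety lies behind it.

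**2. What zero events excludes.** The exact upper limit for 0 of n solves (1 − p)^n = a, so p = 1 − a^(1/n).

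| n | one-sided 95% (a = 0.05) | two-sided 95% (a = 0.025) |
|---|---|---|
| 30 | 9.5% | 11.6% |
| 40 | 7.2% | 8.8% |

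**3. How often this part is met when harm is real.** The chance of no event is (1 − p)^n, if every true event is recorded and attributed.

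| true risk | n = 30 | n = 40 |
|---|---|---|
| 1% | 74.0% | 66.9% |
| 2% | 54.5% | 44.6% |
| 1 in 30 | 36.2% | 25.8% |
| 5% | 21.5% | 12.9% |
| 10% | 4.2% | 1.5% |

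If only half of true events were put down to the dressing (an assumption), the effective risk for the 1-in-30 case is 1 in 60, and the chance of meeting this part rises to about 60% at n = 30 and 51% at n = 40.

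**4. Would the comparative part catch it?** Suppose these events were also counted as complications and usual practice had none. Using Fisher's exact test, two-sided, at 30 per arm: 1 versus 0 gives p = 1.00, 5 versus 0 gives 0.052 and 6 versus 0 gives 0.024. Six events are therefore needed. At a true risk of 1 in 30, the chance of six or more in 30 patients is 0.04%.

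**5. Scale.** Zero events in 59 patients would be needed for a one-sided upper limit of 5%, since 0.95^59 is just under 0.05. About 89 patients would be needed for the chance of missing a 1-in-30 risk to fall to 5%, since (29/30)^89 is about 0.049.

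**The case against.** The strongest reply is that any 30-patient arm has this limit, that the rule is strict because one attributed event fails the dressing, and that the harms the protocol worries about are handled elsewhere. Section 1b names wound infection as the concern. Infection, harmful maceration and deterioration are recorded weekly as variable 9, compared between arms, and backed by blinded photograph review and a blinded physician. This reply stands in part. It confines the point to major events as such, in particular those outside the local wound or not captured as complications. It does not supply the missing bound or comparator.

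Three stronger readings are tempting.

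- A reader might infer that a dressing harming 1 patient in 30 would usually be called safe. It would not: this part fails such a dressing about 64% of the time at n = 30 and 74% at n = 40 if all events are attributed, and the complication part must be met as well.
- A reader might infer that unblinded staff will decide attribution, because section 5 says "it is not possible to blind the participants or the research team members, because they will provide the wound management in this study". The same section says that those verifying closure and complications are blinded, and section 3h sends suspected wound problems to an uninvolved physician who sees the wound without its dressing. The accurate statement is that the assessor of attribution is not named.
- A reader might infer a high false-alarm rate. With a 3% risk in both arms, at least one event would occur in group 2 with probability 1 − 0.97^30, about 60%. That becomes a failure only if every background event is put down to the dressing, which is what the word attributable is there to prevent.

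The data-collection tools are in appendices that were not available, so an adverse-event entry on the forms cannot be ruled out.

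**Conclusion.** The point holds for the major-adverse-event part of the definition. As written, the plan's expected result would be reported as safe although it would exclude only rates above about 12% with 30 patients, or about 9% with 40 (two-sided 95%). A true 1-in-30 risk would go unseen roughly one time in three or four.

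These figures assume 30 to 40 patients in group 2, independent patients, and full recording and attribution of events; under-attribution makes the miss rate larger. The 1-in-30 rate is an illustration.

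The documents do not support a claim that safety is never compared between arms, since local wound complications are. This is a fault in what the trial would be allowed to conclude, which wording and reporting can correct. Neither will give the trial more power to detect rare harm.

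**What to change.** Keep the existing condition as a necessary one and add to it:

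- Count major adverse events of any cause in all three arms, with denominators.
- Report the group 2 rate with its exact (Clopper-Pearson) two-sided 95% interval, and its difference from usual practice with an exact or score interval.
- Word any conclusion with the upper limit, for example: '0 of 30; rates above about 12% excluded'. It should not be worded as absence of major harm.
- In this tabulation, report attribution only as a secondary description and not as a condition for counting.
- Because the retained condition still depends on it, state beforehand what counts as major and who decides attribution.

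The interval should not replace the zero-event condition. Without a threshold no result could fail: 3 of 30 would simply be reported with an upper limit of 26.5%. Nor should the blinded physician be asked to attribute events to a dressing, because that blinding works by hiding which dressing was used.

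The cost is a weaker safety statement, some added recording if the forms lack such an entry, and two intervals in the analysis. No extra patients or visits are needed.
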